9.2.1 Treatment Assignment Procedures

The group allocation ratio is 2:1, 40 BB-12 to 20 control participants. See Section 6.5.3 on Randomization.

The web-based system will integrate the randomization scheme and automatically assign enrolled participants to the corresponding allocation. All research personnel will be naive to group assignments

9.3 Definition of Populations

Statistical analysis on the primary outcome will be performed using the intention to treat principle; all subjects enrolled and randomized will be accounted for in the final analysis in their randomized group.

We will also examine the per protocol group separately and report both the intention-to-treat and per protocol analyses. The mixed effect model will be used, which is compatible with unbalanced outcome measurements. The multiple imputation analysis will be performed when the covariates are missing.

9.4 Interim Analyses and Stopping Rules

Since this is a mechanistic study, analyses of primary and secondary outcome data will not be conducted before the study is completed. The main purpose is to examine the effects of the treatment of BB-12 (on SCFA and microbiome changes), and thus non-inferiority or bio-equivalence testing is not indicated. There will be no interim or futility analysis due to mechanistic aims.

9.5 Outcomes

9.5.1 Primary Outcome

The primary outcome is a difference, measured at day 7, in antibiotic-induced changes in fecal SCFA (with a particular focus on acetate) in participants receiving BB-12-supplemented yogurt versus non-supplemented control yogurt.

9.5.2 Secondary Outcomes

The secondary outcome is a difference, measured at days 7 and 14, in antibiotic-induced changes in the number and diversity of bacteria in the gut microbiota.

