2.4 Likely Mechanisms of BB-12 Health Effects

There are many potential mechanisms by which probiotics are believed to exert their effects. Possible mechanisms of probiotic effect include: 1) production of antimicrobial substances; 2) binding to and penetrating gastrointestinal receptors; 3) competition for nutrients; 4) enhancement of mucosal barrier function; 5) altered immunoregulation, including both anti-inflammatory and immunostimulatory responses; and, 6) ferment glucose, lactose, and fructose, thereby lowering fecal pH.(19-25)

Due to the immune system's role in a multitude of disease states, many studies have concentrated on the immunoregulatory effect of probiotics, examining probiotics' role in diseases, such as eczema with potential mechanisms involving T cell, B cell, epithelial cell, dendritic cell, macrophage, nature killer cell, antibody, and cytokine effects.(26-28) After providing infants who manifested atopic eczema (mean age

of 4.6 months) with a BB-12 infused formula, Isolauri, et al., found significant skin improvements in the probiotic group compared to the control group (P=0.002).(28)

Additionally, many believe that inflammatory bowel disease (IBD) appears to be caused by immune responses to commensal enteric bacteria in predisposed individuals.(24) A commercial blend of eight different probiotic strains (*Streptococcus thermophilus*, three strains of *Bifidobacterium* species and four strains of *Lactobacillus* species), VSL3, has been shown to limit epithelial inflammatory responses in vivo and in vitro, and is often prescribed for individuals with IBD.(29-34)

Further support of an immunoregulatory response is a study conducted by Fukushima et al. on healthy Japanese children between the ages of 15 and 31 months. The children were fed a follow-up formula infused with 10⁹ CFU BB-12 and were found to have a significant increase in total IgA and anti-poliovirus IgA, respectively.(35) This suggests ingestion of the probiotic formula containing BB-12 and colonization by the strain can trigger IgA production by the host. This type of data demonstrates that probiotics positively influence the maturation process of immunity.

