2.5 BB-12 Survival in Stools

The ability to isolate an orally administered probiotic in the stools is considered to be a good indicator that the strain is able to reach key target sites throughout the intestinal tract. The ability of BB-12 to survive intestinal transit has been documented in several studies.(36-39) Taken together, these studies document the ability of BB-12 to survive gastrointestinal transit and persist for 1-3 weeks post feeding. However, the degree of persistence is likely due to doses fed, delivery vehicle, host factors and the ability of BB-12 to grow during colonization. Studies such as the one proposed here are needed to document the success of probiotic survival in foods supplemented with probiotics.

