5. STUDY INTERVENTIONS

5.1 Interventions, Administration, and Duration

The probiotic-supplemented yogurt is composed of the investigational agent, BB-12, and contains the yogurt starter culture YF-L702 (a mixed culture of *Streptococcus thermophilus* and *Lactobacillus delbrueckii* subsp. *bulgaricus*). The yogurt starter culture will be present and alive in the control yogurt. Starter culture alone is unlikely to impact AAD, as it does not survive the acidic stomach environment and is not recovered alive in the feces. Details about yogurt preparation, and enumeration and PCR verification of BB-12 have been previously published and reviewed by the United States Food and Drug Administration (FDA) Center for Biologics Evaluation and Research (CBER).

All participants will take the same amount of either the BB-12 or control yogurt, as determined by random assignment. Participants will each consume a four-ounce daily dose orally for 14 days while on amoxicillin-clavulanate for 7 days. Each four-ounce daily dose of the active yogurt will deliver no less than 10^{10} CFU of BB-12 per day.

Study interventions	BB-12 yogurt and amoxicillin-clavulanate, or Control yogurt and amoxicillin-clavulanate
Administration	Oral, to individual participants
Dosing schedule	4-ounces daily of BB-12 or control yogurt on days 1-14, and Amoxicillin-clavulanate 875/125 mg twice per day on days 1-7
Possible adverse events	See Section 7.3
Setting	Community
Intervention delivery	Research personnel will provide interventions Participants will self-administer
Use of appropriate supportive care, medications or treatments	Not applicable
Dose escalation procedures	Not applicable
Instructions for modifications	Not applicable
Package insert information	See package insert for amoxicillin-clavulanate

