5.2.5 Assessment of Subject Compliance with Investigational Product

DNA extracted from stool samples collected at baseline and at day 7 will be amplified using *B. lactis* specific PCR primers, in order to assess compliance. Participants will not be withdrawn from the study for missed specimen collections but it will be noted in the study file.

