6.2.1.3 Short Chain Fatty Acid (SCFA) Analysis

Primary fecal SCFA produced by anaerobic gut microbiota in the colon (acetate, propionate, butyrate) will be quantified via a liquid chromatography-tandem mass spectrometry assay. Primary fecal SCFA produced by anaerobic gut microbiota in the colon (acetate, propionate, butyrate) will be quantified via a liquid chromatography-tandem mass spectrometry assay. Fecal samples will be homogenized in 50% aqueous acetonitrile, vortex mixed and centrifuged to yield a supernatant containing SCFAs. SCFA in the supernatant are then derivatized with 3-nitrophenylhydrazine to enhance sensitivity of detection. Heavy isotope labeled derivatizing agent (¹³C₆-3nitrophenylhydrazine) is reacted with authentic standards of SCFAs to generate stable isotope-labeled internal standards for each analyte. SCFA will be separated using a Waters BEH C18 (2.1 x 100mm, 1.7micron) UPLC column using an acetonitrile/water/formic acid-based gradient mobile phase where LC-MS/MS analysis will be conducted on either an AB Sciex 5500 QTRAP or a Thermo TSQ QuantumUltra triple quadrupole mass spectrometer operated in negative ion mode.

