9.8 Missing Data

We understand the importance of limiting missing data and as in previous studies the PI and project coordinator will work very closely to prevent missing data. However, there will be some missing data, which we anticipate will be missing at random (MAR). Although it is challenging to test the assumption MAR versus missing not at random (random) due to incomplete information for such test (122), we will carefully examine the missing patterns and perform sensitivity analysis for the MAR assumption (123). The multiple imputation will be used to deal with the missing data (e.g. the missing covariate and baseline outcome variable).

A sensitivity analysis could be used to explore the impact of departures from the MAR assumption underlying the main analysis. For example, we let the mean of observed data and the mean of the unobserved data differ from each other, adjusted for other observed variables. Under an MAR analysis, *the difference* is assumed to be zero. We then evaluate the impact of difference on treatment effect inference under MAR assumption.

To test the secondary hypothesis, we will examine the treatment effects on multiple microbiota composition scores, for example, Bray-Curtis similarity score, Chao1 metric (α -diversity or richness), the Shannon index. We will apply mixed model to analyze these metrics and then perform multiple testing adjustment using FDR and/or FWER correction. The secondary hypothesis analysis is primarily exploratory and will not be used for Go/No Go for R33.

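### The microbiota outcome is read during BB-12 dosing and no stated step separates the product's own reads; product-filtered results would be a cheap addition

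*Combined protocol and SAP*

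**What the plan says.** - **Outcome and timing.** Section 9.5.2 reads the secondary outcome as a difference "measured at days 7 and 14, in antibiotic-induced changes in the number and diversity of bacteria in the gut microbiota". Sections 1.2 and 3.2 give the same two days. The secondary hypothesis in 1.2 also covers days 21 and 30 and return to baseline.
- **Dosing.** Section 5.1 schedules "4-ounces daily of BB-12 or control yogurt on days 1-14" and says the active yogurt "will deliver no less than 10^{10} CFU of BB-12 per day". The live starter culture is in both arms, so BB-12 is the intended bacterial difference between them.
- **BB-12 in stool.** Section 5.2.5 says "DNA extracted from stool samples collected at baseline and at day 7 will be amplified" with B. lactis primers as a compliance check; 5.4 repeats this. Section 2.5 reports that BB-12 can "survive gastrointestinal transit and persist for 1-3 weeks post feeding".
- **Metrics.** Section 9.8 applies mixed models to scores such as "Bray-Curtis similarity score, Chao1 metric" and the Shannon index, with multiplicity correction. Section 6.2.1.4 describes 16S profiling and within- and between-sample comparisons. Neither mentions removing or separately reporting BB-12 or Bifidobacterium reads.
- **Weight.** Section 9.8 calls the secondary analysis primarily exploratory and keeps it out of the R33 decision.

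**The concern.** The mechanistic question is whether BB-12 protects the gut community from the antibiotic. At days 7 and 14 the active arm is swallowing an organism that 16S sequencing will read, and the control arm is not. If its reads stay in the data, a between-arm composition difference mixes two things: a change in the resident community, and the presence of the product. The second is adherence, not mechanism.

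The error can also run the other way. An added organism makes a sample less like that participant's own baseline, so a resident community that was in fact protected would look more disturbed. Section 9.6 would read a null acetate and microbiome result as evidence that BB-12 does not act through the hypothesised mechanisms.

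**Working it through.** The plan gives no power or effect size for this outcome, so there is no figure to reproduce. The check covers timing and then bounds the artefact.

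**Timing.** Days 7 and 14 lie within days 1-14. Table 8 allows ±2 days, so a day-14 sample may fall just after the last serving; hence nominally. Day 21 is 21 − 14 = 7 days after the last yogurt and day 30 is 30 − 14 = 16 days after. The persistence range of 1-3 weeks is 7-21 days, so neither later visit is assured to be free of BB-12.

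**Product share f.** Inputs:
- Viable BB-12 per ml: log 8.49 (week 4) to 8.86 (day 0), Table 6.
- Serving: 100 ml (section 3), or 118 ml for four US fluid ounces.
- Gut total: 10^14, the lower bound in 2.2.
- Assumed: one or two servings present, no growth of BB-12, and 1-, 10- or 100-fold depletion by the antibiotic.

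Low product load s = 10^8.49 × 100 = 3.1 × 10^10. High s = 2 × 10^8.86 × 118 = 1.7 × 10^11. Then f = s / (s + 10^14 / depletion):

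| Depletion | f, low s | f, high s |
|---|---|---|
| none | 0.03% | 0.17% |
| 10-fold | 0.3% | 1.7% |
| 100-fold | 3.0% | 15% |

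Table 6 counts viable cells while sequencing reads DNA, which may understate f. The gut total is a lower bound, which may overstate it.

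**Bray-Curtis similarity to own baseline.** On proportions, similarity is Σ min(p, q), with p the baseline and q the later community. Adding a taxon absent at baseline at share f gives Σ min(p, (1 − f)q). If the rest is unchanged (q = p) this equals 1 − f; in general the loss is at most f. In a simulated community (150 taxa, log-normal abundances, both assumed) similarity fell from 0.648 to 0.614 at f = 0.10 and from 0.647 to 0.532 at f = 0.30. The direction is against protection.

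**Shannon.** The change is h(f) − fH, where h(f) = −f ln f − (1 − f) ln(1 − f). Its maximum is ln(1 + e^(−H)): 0.31 at H = 1, 0.13 at H = 2, 0.05 at H = 3, 0.02 at H = 4. With 5% attrition (38 and 19 evaluable) and two-sided 0.05, 80% power needs d = (1.96 + 0.84) × √(1/38 + 1/19) = 0.79, or 0.39 units at an assumed SD of 0.5. The chance that the largest upward artefact alone reaches significance is 61% at H = 1, 15% at H = 2 and 5% at H = 3. The H = 1 maximum requires f = 27%, above the table's range. A large share lowers H instead: −0.29 at f = 0.30 and H = 3.

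**Chao1.** One extra taxon on 50-200, with an assumed CV of 20-30%, reaches significance about 3-5% of the time, against 2.5% in that direction by chance.

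**Total count.** The change is log10(1 + s / total): below 0.001 undisturbed. At 100-fold depletion it is log10(1.031) = 0.013 to log10(1.17) = 0.07.

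**Taxon level.** If the arms were compared on presence of B. lactis, assumed presence of 50-90% versus 5% gives 98-100% power from the product alone.

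**The case against.** The strongest case against is that the quoted outcome is number and diversity, where the working shows little upward bias unless the community collapses. The Bray-Curtis artefact is conservative for a protection claim. The analysis is exploratory, corrected for multiplicity and outside Go/No Go. Firmicutes qPCR does not count BB-12, and the B. lactis PCR already identifies carriage. All of this stands, and it limits the point to a modest improvement.

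Also fair: no sentence says that all reads are used. Read processing follows cited protocols not reproduced here, and the qPCR text in 6.2.1.5 breaks off in the copy reviewed, so total-count handling cannot be checked.

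Three stronger readings are tempting but unsupported:
- **LEfSe and Metastats will flag the product between arms.** Section 6.2.1.4 assigns these tools to correlations with clinical outcomes, not to the arm contrast. The 98-100% figure applies only if a taxon-by-arm comparison is made.
- **Days 21 and 30 are clean off-product reads.** The protocol's own persistence range covers both.
- **The acetate result has the same flaw and needs butyrate and propionate to agree.** Section 2.4 does list that probiotics may "ferment glucose, lactose, and fructose, thereby lowering fecal pH", but fermentation by BB-12 is still an impact of BB-12, which is what the primary objective asks about. Section 6.2.1.3 already measures all three acids ("acetate, propionate, butyrate) will be quantified via a liquid chromatography-tandem mass spectrometry assay"), and 9.5.1 frames the primary outcome as fecal SCFA with a focus on acetate.

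What the objection leaves untouched is that nothing prespecified separates product from resident community.

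**Conclusion.** The point holds as a cheap improvement. Both named reads fall nominally during dosing, BB-12 DNA is expected in active-arm stool, and no separating step is stated. Between-arm composition differences and any genus- or species-level result involving Bifidobacterium could partly reflect the product. Similarity to own baseline is lowered in the BB-12 arm by up to f, which could hide real protection.

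The size depends on depletion, which the documents do not give: f is about 0.03-0.2% undisturbed and 3-15% at an assumed 100-fold loss. A reader might infer that a positive microbiota result could be nothing more than product detection, or that diversity is biased materially towards protection. The figures do not support either for Chao1, Shannon or total count short of severe depletion. The primary outcome and the R33 decision are not affected.

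**What to change.** In 9.5.2 and 9.8:
- Prespecify Chao1, Shannon, Bray-Curtis similarity to own post-run-in baseline, and any taxon-level analysis in two forms: all reads, and after removing reads assigned to B. animalis. Do this at days 7, 14, 21 and 30.
- Where 16S does not resolve the species, add a sensitivity run removing the whole genus.
- Report the B. animalis read share beside total bacterial number.
- Describe days 21 and 30 as post-dosing, not product-free.
- Base any statement that BB-12 protects the resident microbiota on the filtered results.

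Cost: one bioinformatics filter, SAP wording and a little more analysis; no new samples or assays. The downside is that endogenous B. animalis reads are removed too, and the genus-level run removes all resident bifidobacteria. That is why both forms should be shown.

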9.6 Anticipated Results

The most likely outcomes from the study are:

1. +/- impact of BB-12 on fecal SCFA levels
2. +/- impact of BB-12 on gut microbiota composition (measured to quantify level of disruption achieved by antibiotics as a comparator within this study)
3. +/- impact of BB-12 on AAD (measured, but study not powered to detect clinical difference of AAD).

If BB-12 is found to have a positive effect on the biological signature (acetate levels) as compared to the control, the work to be carried out in the R33 will replicate the R61 methods in a second cohort of

patients, with the addition of timing of probiotic administration, as well as expanding the analysis to characterize the functional microbiome using metatranscriptomic methods. This information will provide a framework for future research in the characterization of other probiotic strains for AAD.

Negative overall group results, i.e. no significant difference between the control and BB-12 groups with respect to longitudinal changes in acetate levels and microbiome composition versus baseline values, will suggest that BB-12 does not impact the gut environment via the mechanisms we hypothesized. However, based on past studies of AAD and BB-12, it is unlikely that we will see no responders to this natural product. However, based on past studies of AAD and BB-12, it is unlikely that we will see no effect of the BB-12 probiotic on maintenance of acetate levels when administered concurrently with antibiotic. Thus, we intend to correlate the changes in acetate levels, by examining the highest and lowest quartiles over time in study participants receiving probiotic to assess whether we can predict the impact of BB-12 using the baseline. Such results will enable fine-tuning of conclusions based on individual responses and suggest new hypotheses for future studies.

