9.2 Sample Size and Randomization

Sample size calculations were informed by data from Hoverstad et al.,(120, 121) which compared changes in the mean SCFA levels between baseline fecal samples and fecal samples collected after six days administration of various antibiotics or placebo in healthy volunteers. In these studies, a mean reduction in acetate levels occurred from 45 ± 16 umol/g at baseline to 24 ± 18 umol/g after antibiotic treatment (46% reduction in acetate). Reductions in acetate after antibiotic treatment ranged from 5% to 79% with ampicillin, a similar antibiotic to amoxicillin.(120, 121) We can infer similar decreases in acetate in our proposed study. Using a conservative estimate of a 42% decrease in acetate in the control/antibiotic treated group and no greater than a 15% decrease in the BB-12 treated group, and an allocation ratio of 2:1 (BB-12 to control volunteers); a total sample size of 60 participants is necessary to have 80% power to detect a significant difference in mean acetate levels as a measure of gut microbiota production of SCFA between a control and BB-12-treated group.

With a sample size of 40 subjects in the active arm and 20 subjects in the control arm and attrition rate of 5% at day six and 20% at day 30, we would have power of 82% to detect a moderate effect size of Cohen's $d = 0.63$ (assuming the intra-correlation correlation coefficient is 0.3). The α level of 0.05 will be used for the analysis. Since the effect size of previous study (reduction in acetate levels) is Cohen's $d = 1.23$, we should have ample power to detect the treatment effect. (The power calculation is based on the R software and packages simr, sjstats, and pwr).

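### Section 9.6 treats a non-significant group difference as evidence against the hypothesised mechanism, but a p-value above 0.05 alone does not separate no effect from the effect the trial is designed to find

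*Combined protocol and SAP*

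**What the plan says.** Section 9.6 (Anticipated Results) describes a negative trial as "no significant difference between the control and BB-12 groups" in the longitudinal changes of acetate and of microbiome composition. It says that such a result, "versus baseline values, will suggest that BB-12 does not impact the gut environment via the mechanisms we hypothesized". The same paragraph then calls a complete absence of effect unlikely and plans an exploratory look at the highest and lowest quartiles of acetate change.

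Section 9.2 supplies the design figures. An alpha "level of 0.05 will be used for the analysis", with sidedness not stated. The plan claims that "we would have power of 82% to detect a moderate effect size" of d = 0.63 with 40 and 20 participants, 5% early and 20% day-30 attrition, and an intraclass correlation of 0.3. It also says that "a total sample size of 60 participants is necessary to have 80% power" for a "42% decrease in acetate in the control/antibiotic treated group and no greater than a 15% decrease in the BB-12 treated group".

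Section 9.1 sets the milestone for moving to R33: an observed Cohen's d of at least 0.6 at day 7 or day 30. Section 9.5.1 puts the primary outcome at day 7. Section 9.7 plans a mixed model on change from baseline over every time point. Section 9.4 remarks that "non-inferiority or bio-equivalence testing is not indicated".

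**The concern.** A non-significant test says that zero is compatible with the data. It does not say that the hoped-for effect is incompatible with them. Section 9.6 moves from the first statement to the second without asking how large an effect the data still allow.

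This is a mechanistic study, so what it says about the mechanism after a null is one of its main products. If the sentence is followed as written, a real effect of the size the trial was planned around could be reported as a sign that the mechanism does not operate. The stake is a mistaken mechanistic conclusion in the report.

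**Working it through.** **Inputs.** Allocation 40:20; attrition 5% early (38:19 left) and 20% at day 30 (32:16 left); intraclass correlation 0.3; alpha 0.05; target d = 0.63 (all 9.2). Acetate is compared with baseline at days 7 and 30, so there are two post-baseline points; milestone d = 0.6 (9.1). Assumption: two-sided test.

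**1. The plan's own figure.** With m = 2 visits, the variance of the group difference in SD units is (1/40 + 1/20) × (1 + 0.3)/2 = 0.075 × 0.65 = 0.0488, so SE = 0.221. Power at d = 0.63 is Φ(0.63/0.221 − 1.96), about 81.4%. This matches the stated 82%, but only with attrition left out. The miss rate implied by the stated power is 100 − 82 = 18%.

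**2. Two-visit mixed model with the stated attrition.** In the BB-12 arm 32 participants have both visits and 6 have one; in control 16 and 3. The information is 32/0.65 + 6 = 55.2 and 16/0.65 + 3 = 27.6. SE = √(1/55.2 + 1/27.6) = 0.233, and the 95% half-width is 1.96 × 0.233 = 0.457. Power at d = 0.63 is Φ(0.63/0.233 − 1.96) = 77.1%, so the miss rate is about 23%. A mixed-model simulation of 600 runs gave 75% power.

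**3. Day 7 alone, 38:19.** SE = √(1/38 + 1/19) = 0.281. With 55 degrees of freedom the critical t is 2.004, so the half-width and the smallest significant d are both 0.563. From the non-central t, power is 59.6% at d = 0.63, a miss rate of about 40%.

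| Analysis of acetate | 95% half-width (SD) | Non-significant if true d = 0.63 |
|---|---|---|
| Plan's stated power | – | 18% |
| Two-visit mixed model, stated attrition | 0.457 | 23% |
| Day 7 alone, 38:19 | 0.563 | 40% |

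**4. The planned percentage contrast.** The cited data fall "from 45 ± 16 umol/g at baseline to 24 ± 18 umol/g after antibiotic treatment". The pooled SD is √((16² + 18²)/2) = 17.03. The planned difference is (0.42 − 0.15) × 45 = 12.15 µmol/g, or d = 12.15/17.03 = 0.71. Day-7 power is then about 70%, a miss rate of about 30%. Across SD 16, SD 18 and a change-score SD of 20.2 (before–after correlation 0.3 assumed), the miss rate is 24%, 34% and 44%.

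**5. Which non-significant estimates are ambiguous.** A 95% interval contains both 0 and 0.6 when the estimate lies between 0.6 minus the half-width and the half-width. At day 7 that is 0.037 to 0.563. In the mixed model it is 0.143 to 0.457.

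**6. What a near-zero estimate can do.** If BB-12 is inert, the upper limit falls below 0.6 in about 55% of trials at day 7 and about 73% in the mixed model with an effect common to both visits.

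**The case against.** Several points on the other side are fair.

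- **The condition is joint.** Section 9.6 asks for a null on acetate and on microbiome composition. The chance of both cannot exceed the chance of the acetate null, so the rates above are upper bounds. This stands. It is not a dependable safeguard, because Section 9.8 calls the microbiome analysis primarily exploratory and multiplicity-adjusted, and no power is stated for it.
- **The day-7 test is not the planned model.** Correct: 9.7 specifies a mixed model over all time points, and for it 18% to 23% is the relevant range. The 40% applies to the day-7 comparison, which is where 9.5.1 places the primary outcome.
- **The wording is soft.** The verb is only a suggestion, and the paragraph goes on to expect some effect and to plan further exploration. That tempers the sentence but gives no precision criterion.

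Two stronger readings are tempting and the documents do not support them. A reader might infer that the trial is too imprecise to separate no effect from the planned effect. It is not: by its own figure it has 82% power at d = 0.63, and step 6 shows that an estimate near zero would exclude d = 0.6. A reader might also infer that a null would close the research line. The R33 milestone in 9.1 is an observed d of at least 0.6 at day 7 or day 30, and no passage makes non-significance a stopping criterion.

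Nor does the remark in 9.4 stand in the way. It concerns formal non-inferiority or equivalence tests and does not prevent anyone from reading a confidence interval.

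**Conclusion.** The point holds in a limited form. Section 9.6 draws a mechanistic conclusion from non-significance alone, and that inference is unsound. With a true acetate effect of d = 0.63, non-significance would arise in about 18% of trials by the plan's own power, about 23% with the stated attrition in a two-visit mixed model, and about 40% at day 7 alone. All three are upper bounds for the joint acetate-and-microbiome condition. Many non-significant estimates are compatible with both zero and the plan's own milestone.

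The figures assume a two-sided test, two post-baseline acetate visits, the stated intraclass correlation and attrition, and equal SDs in the two arms. The percentage-contrast figures also assume that the cited study's SDs apply here. The consequence is a possible misstatement about mechanism in the report; the go/no-go decision does not depend on this sentence.

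**What to change.** Replace the sentence in 9.6 with:

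> A non-significant result will be interpreted from the estimates and 95% CIs of the between-arm acetate difference at day 7 and day 30 from the mixed model. It will be taken as evidence against the hypothesised acetate mechanism only if the upper limits at both visits are below the R61 milestone (d = 0.6); otherwise it is inconclusive.

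Both visits are needed because the hypothesis in 9.1 includes faster recovery and the milestone can be met at either day. A day-7-only rule could exclude the effect in a trial that meets the milestone at day 30. Section 9.4 needs no change.

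No extra participants or data are required. The cost is that more nulls become inconclusive, including many for a truly inert product. Using simple visit-wise intervals, an inert product has its upper limit below 0.6 in about 55% of trials at day 7. At day 30 (32:16, half-width 0.616, so the estimate must be below −0.016) the figure is about 48%. Meeting both therefore happens in at most 48% of trials, and in about 0.55 × 0.48 = 26% if the two estimates were independent; positive correlation puts it in between. In return, if the true effect is d = 0.6 at either visit, the rule would wrongly count against the mechanism in only about 2% of trials.
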